### 2.3. Benefit: Risk Assessments

### 2.3.1 Animal Toxicology

Non-clinical repeated-dose oral toxicity studies in Sprague-Dawley (S-D) rats and cynomolgus monkeys, which may be relevant to human safety, revealed the following toxicities and target organs in the two species as follows:

- In the gastrointestinal (GI) tract: ulcer/erosion in the stomach, duodenum, jejunum, and/or ileum
- In lymphoid tissues: lymphoid depletion
- In lymphoid tissues in S-D rats only: lymphoblastic lymphoma in a non-dose related fashion in 11 of 40 rats at 300 mg/kg (mid-dose) and in 1 of 40 animals at 600 mg/kg (high dose). No cases of lymphoma were observed in the 100 mg/kg/day tazemetostat dose cohort in rats or at any dose cohort (100-600 mg/kg/day) in cynomolgus monkeys treated for 4 or 13 weeks. The etiology and potential human relevance of the rat lymphoma is currently under continued laboratory investigation, but does not appear to be related to alterations in the Notch signaling pathway or endogenous rat leukemia virus reactivation.
- In bone in S-D rats only: there was trabecular bone formation in the femur and sternum in the 4- and 13-week studies
- In the serum of monkeys only: increase of chloride due to bromide derived from the tazemetostat bromide salt formulation (subsequent Phase 1 studies in humans have determined no detectable bromide levels)
- In the liver of monkeys only: hepatocyte and Kupffer cell hypertrophy in the 4-week and 13-week studies, which was accompanied by pigmentation of Kupffer cells and bile duct hyperplasia in some cases in the 13-week study
- In the kidney of monkeys only: glomerulopathy in the 13-week study

Additional animal toxicology is provided in the Investigator's Brochure (IB) for tazemetostat.

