# 4.3. Rules for Suspension of Enrollment

The investigators, IRBs/ECs, regulatory agencies and IDMC will be urgently informed and the IDMC convened to review the data and to make recommendations for potential changes in study conduct if one or more subjects develop any of the following AEs deemed to be definitely related to study treatment by the investigator and/or medical monitor, based upon close temporal relationship or other factors:

- Death
- Anaphylaxis (angioedema, hypotension, shock, bronchospasm, hypoxia or respiratory distress)
- Secondary lymphoma

Should study enrollment be suspended, the study will not be restarted until all parties have agreed to the course of action to be taken and the IRBs/ECs have been notified.

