#### 7.3. **Dose Modification**

No modification of dose is required for the following  $\geq$  Grade 3 non-hematologic toxicities:

- Transient fatigue or asthenia lasting < 24 hours
- Transient myalgia or arthralgia lasting < 24 hours
- Nausea that resolves to < Grade 2 within seven days (with or without anti-emetics)
- Vomiting that resolves to < Grade 2 within 48 hours (with or without anti-emetics)
- Diarrhea that resolves to < Grade 2 within 48 hours

Other toxicities that, in the opinion of the investigator, are possible, probably or definitely related to study treatment, should be managed per Table 3. Toxicities that are felt by the investigator to be unrelated to tazemetostat but clinically significant should be discussed with the medical monitor. In the event of an urgent unrelated toxicity, study treatment should be interrupted as per Table 3. Dose re-escalation is not permitted.

Of note, in the event of an occurrence of a secondary neoplasm, including T-cell lymphoma, study treatment will be permanently discontinued. See Sections 4.3 and 11.5 or further discussion.

occur only after discussion with medical monitor

Dose Adjustmentb Toxicitya **During Therapy** Grade 1 Continue study treatment Maintain dose level All occurrences Grade 2 All occurrences Continue study treatment Maintain dose level **Grade 3c (Not Including Neutropenia)** 1st occurrence Restart at 600 mg BID Interrupt study treatment until 2nd occurrence resolved to Grade ≤1 or baselineb Restart at 400 mg BID (same or new toxicity) 3rd occurrence Discontinue study treatment Not applicable (same or new toxicity) Grade 3 Neutropenia (ANC:  $<1-0.5 \times 10^9/L$ ) Maintain dose level 1st occurrence Interrupt study treatment until Restart at 600 mg BID 2nd occurrence resolved to ANC  $\geq 1.0 \times 10^9/L$ 3rd occurrence Restart at 400 mg BID Discontinue study treatment 4th occurrence Not applicable Grade 4d Resumption of dosing may

**Table 3:** Dose Modifications for Treatment-Related Toxicities

ANC = absolute neutrophil count; BID = twice daily

All occurrences

Hold study treatment

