#### 11.5. Adverse Events of Special Interest (AESIs)

For this study, AESIs will include:

- Occurrence of T-cell lymphoma (refer to Section 11.10 for instructions on continued reporting of these events). Refer to Section 4.3 for management of secondary lymphoma
- Events considered related to abnormal bone formation and confirmed by radiologic scan.

• AEs associated with treatment overdose, misuse, abuse, or medication error; and any treatment-emergent significant laboratory abnormality.

These AESIs are to be captured using the SAE procedures but are to be considered as SAEs only if they met one of the above criteria.

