#### 11.7. Relationship Categorization

A qualified investigator must make the determination of relationship to tazemetostat for each AE or SAE. The investigator should decide whether, in his or her medical judgment there is a reasonable possibility that the event may have been caused by tazemetostat.

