# 11.7.1 Assessing Relationship to Study Treatment

The following should be considered when assessing the relationship of an AE to study treatment:

- Temporal relationship of the onset of the event to the first dose of tazemetostat
- The course of the event, considering especially the effect of discontinuation of study treatment or the reintroduction of study treatment, as applicable
- Whether the event is known to be associated with the study treatment or with other similar treatments
- The presence of risk factors in the study subject known to increase the occurrence of the event
- The presence of non-study treatment-related factors that are known to be associated with the occurrence of the event.

The relationship of an AE to study treatment is to be classified as follows:

- **Not Related:** A causal relationship between tazemetostat and the AE is not a reasonable possibility.
- **Related:** A causal relationship between tazemetostat and the AE is a reasonable possibility (includes probably, possibly and definitely related).

If the causal relationship between an AE/SAE and tazemetostat is related, that determination will be used for purposes of expedited regulatory reporting.

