# 11.9. Timeframe for Reporting AEs and SAEs

**AEs:** AEs will be collected from the time the first dose of study treatment is administered until the earlier of either 30 days after the discontinuation of study treatment or until the initiation of subsequent anti-cancer therapy.

**SAEs:** SAEs will be collected over the same time period as stated above for AEs. In addition, any SAE assessed **as related** to study participation (e.g., protocol-mandated procedures, invasive

tests, or change in existing therapy), study treatment must be recorded from the time a subject provides consent to participate in the study up to and including any follow-up contact. All SAEs will be reported to the sponsor within 24 hours.

After discontinuation of study treatment: The investigator will monitor all ongoing AEs/SAEs until resolution or stabilization of the event or until the subject is lost to follow-up or has withdrawn consent. Up until 30 days after the last dose of study treatment or until the initiation of subsequent anti-cancer therapy, whichever is earlier, the Investigator will report any AE that they consider to be possibly related to study treatment.

Note that any incidence of secondary lymphoma, even if occurring more than 30 days after the last dose of study drug, will be reported to the Sponsor as an SAE.

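### Section 4.3 obliges urgent IDMC convening only for definitely related deaths, anaphylaxis or secondary lymphoma, a causality level that Section 11.7.1 neither defines nor records

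*Combined protocol and SAP*

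**What the plan says.** Section 4.3 (Rules for Suspension of Enrollment) lists three event types: death, anaphylaxis and secondary lymphoma. If one or more subjects develop such an event, and it is "deemed to be definitely related to study treatment by the investigator and/or medical monitor, based upon close temporal relationship or other factors", then investigators, IRBs/ECs, regulatory agencies and the IDMC are told urgently. The IDMC is also convened to review the data and make recommendations. Suspension is not automatic.

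Section 11.7 assigns causality to the investigator: "A qualified investigator must make the determination of relationship to tazemetostat for each AE or SAE". Section 11.7.1 offers two categories. An event is Not Related if a causal link is not reasonably possible, and Related if a causal link "is a reasonable possibility (includes probably, possibly and definitely related"). For a Related event, "that determination will be used for purposes of expedited regulatory reporting".

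For lymphoma, Section 11.5 says: "Refer to Section 4.3 for management of secondary lymphoma". Section 7.3 adds that "in the event of an occurrence of a secondary neoplasm, including T-cell lymphoma, study treatment will be permanently discontinued", and it too points to Sections 4.3 and 11.5. Section 11.9 requires "any incidence of secondary lymphoma, even if occurring more than 30 days after the last dose of study drug" to be reported to the sponsor as an SAE.

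Section 14 gives the IDMC safety data at predetermined times, or ad hoc if needed, without a causality limit. It leaves the review schedule and analysis plan to a separate charter.

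**The concern.** The protocol's only event-specific rule for calling the IDMC together depends on a degree of certainty that its own causality scale does not contain. Someone checking afterwards whether the rule was met would find Related or Not Related in the data, and neither answers the question.

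The bar is also high where the stakes are highest. A death or lymphoma judged probably due to the drug would not oblige the external safety reviewers to meet urgently. Secondary lymphoma deserves particular attention because it was seen in rats, and Section 2.3.1 says of that finding: "The etiology and potential human relevance of the rat lymphoma is currently under continued laboratory investigation". If convening is left to discretion, external review could wait for the next scheduled meeting. The protocol gives no dates for those meetings, and no other event-specific rule pauses enrollment in the meantime.

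**Working it through.** The documents attach no figure to this rule, so there is nothing to reproduce. The check sets the sections side by side.

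**1. What Section 4.3 needs.** One event of a listed type in one subject; a judgement of *definitely* related; made by the investigator, the medical monitor or both; on close timing or other factors. The factors are not specified.

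**2. What Section 11.7.1 records.** Mapping the three degrees of certainty onto the two sections:

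- Possibly related: recorded as Related; Section 4.3 not triggered.
- Probably related: recorded as Related; Section 4.3 not triggered.
- Definitely related: recorded as Related; Section 4.3 triggered.

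The same recorded value covers both outcomes, so the trigger is not a function of recorded causality. It needs a second judgement for which the protocol gives no definition and no recorded level. The medical monitor's view is not part of the Section 11.7 determination either.

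**3. How causality is used elsewhere.** Section 7.3 sends possibly, probably and definitely related toxicities alike to Table 3. Most Grade 3 toxicities judged possibly related therefore interrupt treatment. Section 11.7.1 ties expedited reporting to the pooled Related category. Section 4.3 alone separates out the top degree.

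**4. Secondary lymphoma.** The one criterion that Section 4.3 names is a close temporal relationship. Section 11.9 provides for lymphoma arising more than 30 days after the last dose, which that criterion suits poorly. Section 2.3.1 reports lymphoma in 11 of 40 rats at the middle dose and 1 of 40 at the high dose, and Section 2.3.4 carries lymphoma forward as a potential risk. Sections 7.3 and 11.5 both direct the reader to Section 4.3, and neither adds an IDMC trigger of its own.

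**5. What a probably related death or lymphoma does set off.**

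- Permanent discontinuation for that subject, if a secondary neoplasm (Section 7.3).
- SAE report to the sponsor within 24 hours, and regulatory reporting within 7 or 15 days if it qualifies as a SUSAR (Section 11.10).
- Notice to the IRB/EC, as for every SAE at the site (Section 11.10.1).
- Inclusion in the safety data that the IDMC sees at its next predetermined review, or sooner if someone decides that an ad hoc review is needed (Section 14).

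The one step missing from this list is an obligation to convene the IDMC urgently, together with the urgent notices that Section 4.3 attaches to it.

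**The case against.** The strongest reply is that the other safeguards are wide and that reserving a multi-party alert for high-certainty cases is a legitimate choice. Eligibility asks only for a life expectancy above three months (Section 5.2), so deaths are expected, and a loose trigger under a heading about suspending enrollment could produce many alerts. Section 15.7 also lets the sponsor stop the study for a safety hazard. Much of this stands, and it limits the point to urgent convening. It does not justify a trigger whose level is undefined. Deaths judged Not Related, such as those attributed to mesothelioma, would stay outside a trigger set at Related.

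A reader might infer that a probably related death or lymphoma escapes IDMC review altogether. The documents do not support that. Section 14 commits the IDMC to predetermined safety reviews whatever the causality, and it may recommend a hold or termination without any finding of definite relatedness.

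A reader might also infer that no single case in a single-arm trial could ever be called definite, or that the rule cannot be operated. Neither follows. Section 11.7.1 rests causality on timing, the effect of stopping or restarting the drug, known association and other risk factors, not on cohort incidence. Section 4.3 also lets either of two parties make the call. The trigger is undefined but usable.

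Finally, the charter may already contain a lower ad hoc threshold. That cannot be excluded.

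**Conclusion.** The point holds in a limited form. Urgent notification and IDMC convening are mandatory only at a causality level that the protocol does not define or record. For a listed event judged possibly or probably related, the IDMC's involvement rests on scheduled or discretionary review.

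The size is qualitative: three event types, and the two lower of the three degrees that Related pools. The documents give no rate of related deaths, anaphylaxis or secondary lymphoma for this population, so neither the number of events missed by the trigger nor the number of extra meetings under a wider one can be derived.

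The conclusion assumes that the charter sets no lower trigger. It also reads the terms in parentheses after anaphylaxis (such as hypoxia and respiratory distress) as manifestations of anaphylaxis, not as separate triggers. This is a cheap improvement to safety oversight, not a failure of safety reporting.

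**What to change.** In Section 4.3, replace the words "deemed to be definitely related to study treatment by the investigator and/or medical monitor, based upon close temporal relationship or other factors" with: *classified as Related by the investigator (Section 11.7.1), or considered by the medical monitor to have a reasonable possibility of being related*.

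Keep the three event types, state that the parenthetical terms are manifestations of anaphylaxis, and keep IDMC review without automatic suspension. If the charter already holds such a trigger, cite it in Section 4.3 and align the wording.

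The cost is one sentence in an amendment. The investigator's part uses the classification already collected. The medical monitor's part needs a short written note for these three event types. Because the same sentence governs urgent notice to investigators, IRBs/ECs and regulators, the change brings some additional notices as well as ad hoc IDMC meetings.

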# 5. STUDY POPULATION

## 5.1. Target Population

This study will be conducted in up to 12 subjects (Part 1) and 55 subjects (Part 2) with malignant mesothelioma (pleural, peritoneal, pericardial, tunica vaginalis).

#### 5.2. Inclusion Criteria

A subject must meet the following criteria to be eligible for entry into the study:

- 1. Age (at the time of consent)  $\geq$ 18 years of age
- 2. Has an Eastern Cooperative Oncology Group (ECOG) performance status of 0 or 1
- 3. Has a life expectancy of >3 months
- 4. Has mesothelioma (pleural, peritoneal, pericardial, tunica vaginalis) of any histology that is relapsed or refractory after treatment with at least one pemetrexed-containing regimen
- 5. Has a documented local diagnostic pathology of original biopsy confirmed by a Clinical Laboratory Improvement Amendments (CLIA)/College of American Pathologists (CAP) or equivalent laboratory certification
- 6. Part 2: Molecular evidence of BAP1 loss of function present on local pathology, e.g., lack of nuclear BAP1 staining by immunohistochemistry (IHC)
- 7. Has sufficient archival tumor tissue (a minimum of 10 slides or tumor block) available for central retrospective testing of BAP1 status
- 8. Has all prior treatment (i.e., chemotherapy, immunotherapy, radiotherapy) related clinically significant toxicities resolve to ≤ Grade 1 per CTCAE, version 4.03 or are clinically stable and not clinically significant, at time of enrollment
- 9. Prior therapy(ies), if applicable, must be completed according to the criteria below prior to first dose of tazemetostat:
  - a. Cytotoxic chemotherapy; at least 21 days since last dose
  - b. Non-cytotoxic chemotherapy (e.g., small molecule inhibitor); at least 14 days since last dose
  - c. Monoclonal antibody; at least 28 days since the last dose
  - d. Non-antibody immunotherapy (e.g., tumor vaccine); at least 42 days since last dose
  - e. Radiotherapy, at least 14 days from last local site radiotherapy

- f. Hematopoietic growth factor; at least 14 days from last dose
- g. Investigational drug; 30 days or five half-lives, whichever is longer, from last dose
- 10. Has measurable disease based on either modified RECIST [Nowak 2005] for thoracic disease or RECIST 1.1 elsewhere
- 11. Has adequate hematologic (bone marrow and coagulation factors), renal, and hepatic function as defined by criteria below:
  - a. Hemoglobin ≥9 g/dL
  - b. Platelets  $\ge 100,000/\text{mm}^3$  ( $\ge 100 \times 10^9/\text{L}$ ) without platelet transfusion for 7 days
  - c. ANC  $\geq 1000 / \text{mm}^3$  ( $\geq 1.0 \times 10^9 / \text{L}$ ) without growth factor support for 14 days
  - d. Coagulation: Prothrombin time (PT) <1.5  $\times$  ULN and partial thromboplastin time (PTT) <1.5  $\times$  ULN
  - e. Creatinine  $< 2.0 \times ULN$
  - f. Hepatic function: Total bilirubin  $<1.5 \times ULN$  and ALT and AST  $<3 \times ULN$
- 12. Has a QT interval corrected by Fridericia's formula (QTcF) ≤480 msec
- 13. Willing to provide tissue for translational research
- 14. Female subjects of childbearing potential must have a negative urine or serum pregnancy within 72 hours prior to receiving the first dose of study drug; if the urine test is positive or cannot be confirmed as negative, a serum pregnancy test will be required and subject also should agree to use an adequate method of contraception starting with screening through 30 days after the last dose of study therapy (if sexually active).
- 15. Male subjects should agree to use condoms starting with the first dose of study therapy through 30 days after the last dose of study therapy if sexually active with a female of childbearing potential

#### 5.3. Exclusion Criteria

A subject who meets any of the following criteria is ineligible for entry into the study:

- 1. Has had prior exposure to tazemetostat or other inhibitor(s) of enhancer of zeste homologue-2 (EZH2)
- 2. Has a history of known central nervous system metastasis
- 3. Has had a prior malignancy other than the malignancies under study

- **Exception:** A subject who has been disease-free for 5 years, or a subject with a history of a completely resected non-melanoma skin cancer or successfully treated in situ carcinoma is eligible.
- 4. Has had major surgery within 3 weeks prior to enrollment (a percutaneous biopsy, pleural catheter insertion, placement of central venous catheter or other minor procedure are permitted)
- 5. Is unwilling to exclude grapefruit juice, Seville oranges and grapefruit from the diet and all foods that contain those fruits from time of enrollment throughout their time on study
- 6. Has cardiovascular impairment, history of congestive heart failure greater than NYHA Class II, uncontrolled arterial hypertension, unstable angina, myocardial infarction, or stroke within 6 months prior to the planned first dose of tazemetostat; or ventricular cardiac arrhythmia requiring medical treatment
- 7. Is currently taking any prohibited medication(s)
- 8. Has an active infection requiring systemic treatment
- 9. Has a congenital or acquired immunodeficiency, including subjects with known history of infection with human immunodeficiency virus (HIV)
  - **NOTE:** HIV-positive subjects who are taking antiretroviral therapy are ineligible due to potential PK interactions with tazemetostat.
- 10. Has known history of chronic infection with hepatitis B virus (hepatitis B surface antigen positive) or hepatitis C virus (detectable anti-hepatitis C circulating viral RNA)
- 11. Has had a deep venous thrombosis (DVT) or pulmonary embolism within the 2 weeks prior to study enrollment.
  - **NOTE:** Subjects with a history of a DVT or pulmonary embolism > 2 weeks prior to study enrollment who are on anticoagulation therapy with low molecular weight heparin are eligible for this study.
- 12. Is pregnant of breastfeeding

# 6. INVESTIGATIONAL PRODUCT

## 6.1. Description

Tazemetostat (EPZ-6438) is an Epizyme investigational product (IP) and is defined as an Investigational Medicinal Product (IMP) under the European Union Clinical Trials Directive (EU CT Dir).

The contents of the package label will be in accordance with all applicable regulatory requirements. The expiry date will be printed on the label.

Tablets will be provided in 200 mg and 400 mg strengths. The 400-mg tablets will be used as primary treatment; however, if the median  $C_{max}$  of the 400-mg tablets in Part 1 of the study is greater than twice the median  $C_{max}$  observed with the 200-mg tablets used in the E7438-G000-101 FIH study, the 200-mg tablets will be considered for use in Part 2 of the study. The 200-mg tablets will be used when a dose reduction to 600 mg is required.

	Investigational Product	
Product name	Tazemetostat (EPZ-6438)	
Formulation description	200-mg tablet, 400-mg tablet	
Dosage form	Tablet	
Physical description	The 400-mg tablets are red, modified oval, biconvex, film-coated tablets with a length of approximately 18 mm. The 200-mg tablets are red, round, biconvex, film-coated tablets with a diameter of approximately 10 mm. Each strength is packaged in white high-density polyethylene bottle with a child resistant, tamper-evident polypropylene screw cap.	
Dose/Route/Schedule/Duration	800 mg/Oral/ BID/Continuous	

